6.3 Screening Criteria

Participants will be recruited at participating sites from the GI and Allergy clinics, or other clinics in which patients with EoE are often seen. In addition, potential participants will be identified through the EGID database (CCHMC IRB studies #2008-0090 and 2008-0098). The research information will be entered into a databank on www.clinicaltrials.gov, maintained by the U.S National Library of Medicine (NLM) at the National Institutes of Health (NIH), and may be advertised on other websites (CCHMC web pages, such as the Cincinnati Center for

Eosinophilic Disorders website, the RDCRN webpage, etc.).

During screening (within twelve weeks of enrollment), a diagnosis of active EoE will be confirmed. Participants will be initially screened for the following:

1. Age between 6 and 17 years
2. An EGD with biopsies performed within twelve weeks prior to enrollment documenting active EoE (\geq 15 eosinophils/hpf)
3. PPI confirmed EoE. As a part of the diagnosis of active EoE, it must be demonstrated that acid reflux disease is not the primary cause of the participant's symptoms by documentation that the participant has been on a high dose of PPI (at least one dose, once daily), for at least 6 - 8 weeks prior to a diagnostic endoscopy of EoE without histologic resolution (i.e., \geq 15 eosinophils/hpf). (Due to the variety of doses and various proton pump inhibitors available, the dose and adherence will be confirmed adequate at the discretion of the principal investigator).

Participants who meet the screening entry criteria of EoE will be enrolled in the study. An EGD and biopsy results will be accepted as baseline if done within twelve weeks prior to the enrollment visit and there have been no changes in either dietary or pharmaceutical treatment during that pre-screening interval. If the participant is on a current dose of acid reflux therapy (e.g., PPIs or histamine H₂ receptor antagonists), the participant will continue his/her acid reflux therapy as long as the dose remains the same throughout the study. Screening exclusion criteria for patients entering the study include the presence of hypereosinophilic syndrome, parasitic infection, inflammatory bowel disease, Celiac disease, *Helicobacter pylori* infection, and patients who are currently on dietary therapy avoiding milk (i.e. on a 1FED) or milk, egg, soy, and wheat (i.e. on a 4FED). Ideally we would like to exclude patients with a history of diet and/or SGC therapy as knowing the results could bias selection of patients into the trial. However, in clinical practice most patients have already tried diet and/or steroid therapy by the time they are seen in EoE specialty clinics. In these situations, true compliance and efficacy of treatment are typically not clear. Narrowing the study to newly diagnosed patients is not practical. As such, we will exclude patients with known definitive response to diet and/or SGC, such as participation in prior clinical trials. In addition, patients cannot have been on topical swallowed steroids within the last 2 months or systemic steroids within the last 3 months prior to enrollment. Participants may continue any inhaled steroids needed for asthma control as appropriate. We have selected the 6-year lower age range to minimize concern about compliance with and safety of the SGC in Phase II. The 17-year old upper age range was selected to align with the age ranges supported by our instruments measuring quality of life and patient symptom scores.

All protocol-required study procedures, including efficacy and safety assessments are summarized in Table 1 in the Study Visits and Assessments Section.

6.4 Safety

Safety will be monitored by physical exam findings at the screening visit, at the visit on the day of the endoscopy at the end of Phase I (12 weeks), and again at the end of Phase II (week 25) for those who fail to respond to the dietary therapy. In addition, for those who receive SGC during Phase II, morning cortisol will be checked at the beginning and end of Phase II to monitor for adrenal suppression. No additional endoscopies beyond the standard of care will be required for participation in this study, and no more than 4 additional biopsies will be obtained for research during endoscopy. Blood draws will occur whenever possible with the start of the IV for endoscopy. In addition, adverse events will be monitored from when informed consent is signed, at each visit, and throughout the study.

The PI at each performance site will review all unexpected and study-related events and forward their assessments to the CCHMC PI and study sponsor for review. Finally, privacy and confidentiality will be maintained according to HIPAA guidelines. These and other risks are reviewed in the Informed Consent and approved by the central IRB.

6.5 Efficacy

6.5.1 AIM 1: To Determine The Efficacy Of A 1FED Vs. 4FED In EoE

6.5.1.1 Primary End-Point

The primary efficacy endpoint will be the change in PEES v2 as measured prior to initiation of the study diet and at the end of Phases I & II^{1, 20}. The PEES v2, a validated PRO metric, measures clinical symptoms in EoE that broadly fall into four categories: dysphagia, gastrointestinal reflux disease, nausea/vomiting, and pain. We hypothesize that therapeutic interventions will improve clinical symptoms as measured by PRO metrics and 4FED will be more effective than a 1FED with this measurement. This is an important issue to resolve as only a few prior studies have shown the clinical efficacy of therapeutic interventions, and these have been mainly in adults. In fact, several studies have shown dissociation between histology (eosinophil levels) and clinical improvement^{20, 21}, but these studies have not used validated metrics for measuring symptoms. We will therefore employ validated EoE specific measurement tools (Pediatric EoE Symptom Score (PEES Version 2.0) (used as the primary endpoint) and Pediatric EoE Quality of Life (Ped EoE QL)) metrics using parent reported outcomes by proxy for patients^{1, 20, 22, 23} to measure the clinical efficacy of our therapeutic interventions and to correlate symptoms with histology. The measurement of pre/post diet symptoms using tools that have

undergone at least some validation in pediatric patients is a novel aspect of our study. Agreement about these measurement tools has significant bearing on the eventual FDA approval of therapeutic agents²⁴

6.5.1.2 Secondary End-Point Analysis: Histology And Endoscopy

At the end of each phase, we will employ generic Health Related QOL metrics, such as PROMIS General Health Questionnaire and Peds-QL and eventually compare the changes in disease specific versus general health questionnaires. These PROs will be assessed at the screening visit and again at the end of each treatment phase to assess the effects of treatment. All participants will undergo EGD with biopsy and the percentage of patients who have <15 peak eosinophils/hpf will be determined. The slides will be reviewed by local pathologists for clinical purposes, who will be blinded to the treatment group and patient study number. The local pathology review will be used to determine whether or not participants continue into Phase II of the study. Participants with ≥ 15 peak eosinophils/hpf who were on 4FED during Phase I will continue into Phase II to receive SGC for three months while on an unrestricted diet. Participants with ≥ 15 peak eosinophils/hpf who were on 1FED during Phase I will also continue into Phase II, but will maintain the 4FED therapeutic diet for 3 months. The Central Review Pathology Committee (CRPC), who will also be blind to the treatment group, will subsequently review the esophageal biopsy slides to determine other parameters (such as the Histology Scoring System (HSS)). CRPC review will be completed, whenever possible, within 2 weeks of a subject's endoscopy. . Participants who achieve histologic remission at the end of Phase I (as determined by the local pathology review) will have completed the study and will resume follow-up care with their primary gastroenterologist or allergist. Peak eosinophil change will be measured and we will also aim to determine the percentage of patients who achieve remission, defined as both complete remission (≤ 1 peak eosinophils/HPF) and partial remission (<10 and <6 peak eosinophils/HPF) as reported¹¹; this will allow us to compare with other studies that have used 6FED^{16, 19, 25, 26}. Furthermore, we aim to more broadly examine the impact of each therapeutic intervention on other histological parameters associated with EoE using a quantitative histology scoring system (HSS) that has been developed by our expert pathologist, [name]. The HSS evaluates esophageal biopsies for various features (ex: basal layer hyperplasia, dilated intercellular spaces, surface epithelial alteration, apoptotic epithelial cells), eosinophilic inflammation (peak count, eosinophil abscess, eosinophil surface layering), and lamina propria (fibrosis). For central review, slides of relevant esophageal biopsies obtained during the course of the study will be scanned using an Aperio Imaging scanner and viewed by the CRPC using Aperio Imaging Software. Each member of the CRPC has access to an Aperio scanner in his or her pathology department and to the Aperio Imaging Software. Slides may be scanned into Aperio at the local site, or they may be sent to Cincinnati Children's Hospital Medical Center (CCHMC) to be scanned into Aperio (if the local site does not have an Aperio scanner). These slides will be returned to the local site once they have been

scanned in. A password-protected website housing the scanned images will be created at CCHMC, and the CRPC will have access to that site. A secure image repository may also be housed at the Data Management Coordinating Center of the Rare Diseases Clinical Research Network at the University of South Florida. The central review pathologists will establish interobserver and intraobserver variability in their evaluation of eosinophils and other pathologic features: The central pathologists will re-count eosinophils in the scanned images of biopsies that they previously reviewed at their microscope and compare the peak eosinophil counts that they obtained by viewing the scanned images to evaluate the variability in the counts. The CRPC pathologists will compare their results amongst themselves and resolve differences via teleconferences in which the scanned images are displayed (meetings hosted by GoToMeeting or equivalent sites). Ten percent intraobserver and interobserver variability will be considered optimum. Each review pathologist will review study slides from subjects enrolled at their own institution ([name], CCHMC; [name], CHCO; [name], NW). Relevant biopsy slides from the other participating sites will also be reviewed by the CRPC. The workload will be distributed as equally as possible among the CRPC pathologists with the assistance of the DMCC. Gastric and/or duodenal biopsies will only be reviewed by local clinical pathologists and will not be sent to the CRPC for review, except for cases where a participant's diagnosis is unclear (for example, when it is unclear whether a potential participant does or does not have eosinophilic gastritis or colitis). In such cases, the CRPC will review gastric and/or duodenal slides to confirm the appropriate diagnosis. Subjects may be included, without stomach or duodenal biopsies, if there is no clinical history of involvement of stomach or duodenum. We hypothesize that HSS will more accurately quantify changes associated with EoE and be reversible following each therapeutic intervention. Furthermore, we hypothesize that some patients may show partial responses, where a subset of the HSS may be improved earlier or in dissociation with eosinophil levels, for example. Finally, we will aim to determine the impact of the various therapeutic interventions on gross endoscopic changes, as determined by a recently developed endoscopy scoring system (EREFS) developed by [name] and colleagues²⁸.

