5.2 Secondary Objectives

- To extend Phase I of this study with a prospective non-blinded trial that determines the rate of remission after treatment with 4FED (in participants failing 1FED in Phase I) or SGC (in participants failing 4FED in Phase I) (Phase II).
- To evaluate the effect of each therapy on histological remission (defined as a post therapy eosinophil count of <15 eosinophils/HPF) and by a variety of changes in eosinophils, including (a) pre- and post-therapy peak eosinophil counts; (b) partial remission (2-14 peak eosinophils/hpf); and (c) complete histological remission (≤ 1 peak eosinophils/hpf).
- To evaluate the effect of each therapy by utilizing the histology scoring system (HSS) created to express the severity and extent of other abnormalities in the gastrointestinal (GI) tract that often accompany eosinophilic inflammation.
- To determine the impact of each therapeutic intervention on biomarkers using the EoE Diagnostic Panel (EDP).
- To evaluate the clinical and psychosocial effect of each therapy using the Peds Quality of Life Inventory Eosinophilic Esophagitis Module (PedsQL EoE) to assess EoE symptoms and problems/feelings related to eating.
- To determine if any clinical parameters predict response to therapeutic intervention.
- To determine if any biomarkers including component-resolved diagnostics (CRD) [serum IgE component testing] predict response to therapeutic intervention.
- To determine if skin testing, in the form of prick and patch testing, predicts response to therapeutic intervention.

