6 INVESTIGATIONAL PLAN / OVERALL STUDY AND PLAN

6.1 Number Of Participants

We will be recruiting a total of 292 participants, approximately 50 participants between the ages of 6-7 years of age will be enrolled, approximately 120 participants between the ages of 8-12 years of age will be enrolled, and approximately 120 participants between the ages of 13-17 years of age will be enrolled, to enter this study based

on the presence of active eosinophilic esophagitis and adherence to the inclusion and exclusion criteria. The DMCC at the University of South Florida Health Informatics Institute will serve as the central data management center, with CCHMC serving as the primary site and the central IRB. Additional sites include: Children's Hospital of Colorado, Riley Hospital for Children, Children's Hospital of Philadelphia, University of California at San Diego/Rady Children's Hospital, Northwestern University/Lurie Children's Hospital, Tufts Medical Center, Mt. Sinai Kravis Children's Hospital, Arkansas Children's Hospital, and the University of North Carolina.

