7.6 Phase II Visit 1 (Week 13)

Those participants who have completed the Phase I diet protocol but have continued active inflammation will return to clinic once their biopsies have been read, within 1 week of their EGD. At this visit, the following procedures will occur:

- Measure vitals (blood pressure, heart rate, respiratory rate, temperature), height and weight
- Assess AEs
- Assess participant compliance with concomitant medications
- Provide standardized instructions for administration of the fluticasone for those moving on to SGC
- Provide standardized instructions for 4FED to participants who will be on 4FED
- Provide diet or medication diary/log to participants

PCORI Diet Study

- Administer dietary questionnaire to all participants to measure *intake* of the food allergens. Review food diary (from Visit #5) for those who will be on 4FED
- Dispense the fluticasone to the participant for those moving on to SGC
- Measure morning cortisol (serum, ~1 tsp or 5 mL) for those moving on to SGC

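### Central histology readers are blinded to diet but not to visit, and at seven of ten sites one child's slides may go to different readers; this may bias within-therapy HSS change and adds noise to it.

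*Protocol*

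**What the plan says.** **Blinding.** Protocol 6.5.1.2 names one thing that is hidden from central readers: "The Central Review Pathology Committee (CRPC), who will also be blind to the treatment group". Neither document says that visit is masked, that reading order is randomised, or that slides are batched.

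**Timing.** The same section says that "CRPC review will be completed, whenever possible, within 2 weeks of a" child's endoscopy. Endoscopies fall at screening, week 12 and, for Phase I non-responders, week 25 (Table 1).

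**Allocation.** Three sites have a CRPC member, and there "Each review pathologist will review study slides from subjects enrolled at their own institution". For the remaining sites, "The workload will be distributed as equally as possible among the CRPC pathologists with the assistance of the DMCC". Section 6.1 lists ten sites, so seven have no CRPC reader of their own.

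**Reader agreement.** Section 6.5.1.2 has readers establish intra- and interobserver variability, settle differences by teleconference, and treat ten percent variability as optimum. It sets no action if that is missed.

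**What the reads are for.** Assessing each therapy's effect through HSS is a secondary objective (Protocol 5.2; SAP Secondary Objectives). The SAP adds the relation between PEESS change and HSS. Entry to Phase II rests on the local read: "The local pathology review will be used to determine whether or not participants continue into Phase II of the study". Section 7.6 has those children back in clinic quickly: they "will return to clinic once their biopsies have been read, within 1 week of their EGD".

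**The concern.** HSS is used as a before-after measure, and the protocol states the direction it expects: the abnormalities should reverse after each therapy. A reader who knows or guesses that a slide is post-treatment may score it lower. Several listed features, such as surface epithelial alteration and dilated intercellular spaces, appear to call for judgement, so expectation could influence them.

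The exposure is greatest in Phase II. 4FED after failed 1FED, and swallowed steroid after failed 4FED, are non-randomised groups without a comparator, so nothing in the design would offset a shift tied to visit.

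Separately, when two readers score one child's slides, the difference between the readers enters that child's change score. This widens intervals for HSS change, including in the randomised comparison, and weakens the association with PEESS change. The SAP's models allow for clustering by site and name no reader term. With about 50 children expected (SAP 4.1), there is little precision to spare.

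The two-week target buys nothing for routing. The local read decides Phase II, and the Phase II visit is due within 1 week of the endoscopy, before the central read is due.

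**Working it through.** The plan gives no figure for HSS variability, reader variance or HSS power, so there is none to reproduce. The calculations below rest on assumptions and show ranges.

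**1. Who is exposed to mixed readers.** Ten sites less three with a CRPC reader leaves seven. Assuming equal enrolment by site, 7/10 = 70% of children are at those sites.

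**2. Added variance of change.** Take the between-child SD at one visit as 1 and the pre-post correlation as 0.5 (assumed). With one reader per child, the variance of change is 2 × (1 − 0.5) = 1. Let reader offsets have SD s = 0.3 to 0.5 (assumed). Two different readers add 2s². With three readers allocated at random, a pair of slides has different readers with probability 2/3. The average added variance is 0.70 × (2/3) × 2s²:

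- s = 0.3: 0.70 × 0.667 × 0.18 = 0.084, or 8%
- s = 0.5: 0.70 × 0.667 × 0.50 = 0.233, or 23%

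**3. In children.** The equivalent loss from 50 is 50 × (1 − 1/(1 + added)):

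- 50 × (1 − 1/1.084) = 3.9, about 4
- 50 × (1 − 1/1.233) = 9.5, about 9

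**4. Sensitivity.** Let readers account for a share r of the variance of a single score, and let ρ be the pre-post correlation of the rest. The variance ratio is 1 + 2r(0.70 × 2/3) / [2(1 − r)(1 − ρ)].

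| r | ρ | Variance ratio | SD ratio |
|---|---|---|---|
| 0.05 | 0.3 | 1.035 | 1.017 |
| 0.10 | 0.5 | 1.104 | 1.051 |
| 0.20 | 0.5 | 1.233 | 1.111 |
| 0.20 | 0.7 | 1.389 | 1.179 |

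**5. Visit-related shift, before-after.** Suppose there is no true change and knowing the visit shifts follow-up scores by 0.2 to 0.4 SD of the change (assumed). The chance that a two-sided 5% paired t-test rejects (noncentral t, noncentrality = shift × √n) is:

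| n | Basis | Shift 0.2 | Shift 0.4 |
|---|---|---|---|
| 25 | one Phase I arm, 50/2 | 16% | 48% |
| 14 | 1FED failures, 25 × 0.55 | 11% | 28% |
| 9 | 4FED failures, 25 × 0.35 | 8% | 19% |

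The failure fractions come from the 45% and 65% response rates in Protocol 12.1. The SAP specifies no such paired test, so these rates only illustrate how far a shift could mislead.

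**6. Visit-related shift, between arms.** In 20,000 simulated two-sample t-tests with 25 per arm and no true difference, rejection was 5.0% with a 0.3 SD shift in both arms and 5.1% with none. A common shift cancels.

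**The case against.** The other side has several good points.

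- **Timing alone does not reveal visit.** Slides arrive in visit order only within a child. Ten sites enrolling over a study of two to three years send baseline, week 12 and week 25 slides mixed together. The two-week target applies only where possible, and a baseline endoscopy may predate consent or come from an outside institution (7.2). Samples and data are to be de-identified. Nothing says that readers see visit labels. This stands: the documents support a possible bias, not an established one. The gap is that nothing requires visit to be hidden.
- **A reader might infer that the randomised comparison is biased.** It is not. Readers are blind to diet, so a shift common to both arms cancels. Only noise remains.
- **A reader might apply the reader-mixing penalty to all 50 children**, giving 12% to 33% more variance, or about 5 to 12 children. The documents do not support that, because children at the three CRPC sites keep one reader. The penalty also shrinks below 8% to 23% if those sites enrol more than their equal share.
- **A reader might take the false-positive rates as the trial's error rates.** The SAP compares arms on secondary endpoints by mixed model and, for Phase II, specifies only remission rates with confidence intervals.
- **Reader agreement is addressed.** The variability exercise and teleconferences help. Their worked detail concerns eosinophil re-counts, and they neither mask visit nor keep a child with one reader.

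**Conclusion.** The concern holds as a gap in the conduct of a secondary endpoint. Visit is not masked for central readers, and at seven of ten sites nothing keeps a child's slides with one reader. The first may bias within-therapy HSS change, with most at stake in the two uncontrolled Phase II groups. The second adds noise to change scores, including those in the randomised comparison.

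The noise is about 8% to 23% of the variance of change, on assumed reader offsets, an assumed correlation of 0.5 and equal enrolment by site. The size of any visit-related bias cannot be derived from the documents. It would distort reported mean changes whether or not a test is run.

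PEESS is parent-reported and Phase II entry uses the local read, so neither is affected. The change is worth making because it is cheap, but the trial's main conclusion does not depend on it.

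**What to change.** Amend Protocol 6.5.1.2 so that:

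1. The DMCC assigns all of one child's slides to one CRPC reader, balancing workload by child rather than by slide.
2. Visit labels and dates are removed from the scanned images.
3. Slides for the analysis read are released in random order, mixed across children and visits, in place of the two-week target.
4. Rapid CRPC review stays for the eligibility queries in 7.2, and those slides are re-read masked for the analysis.

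Slides should not be released as a complete set per child. Among completers, two endoscopies mean Phase I remission and three mean failure, so the size of the set gives away the outcome, and seeing the slides together makes their order easier to guess. Masking will still be imperfect, because baseline slides show active disease by inclusion criterion.

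The cost is small. Central HSS results arrive later, which does not affect routing, and a few eligibility slides are read twice. The images, the readers and the DMCC's role in allocation are already in place, and slides already read in sequence can be re-read masked from the scans.
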